MEXICAN SOCIAL SECURITY INSTITUTE
EDUCATION, RESEARCH AND HEALTH POLICY UNIT
HEALTH RESEARCH COORDINATION
HIGH SPECIALTY MEDICAL UNIT (UMAE) "DR. BERNARDO SEPÚLVEDA"
CENTRO MÉDICO NACIONAL SIGLO XXI, IMSS, CDMX.
MEDICAL RESEARCH UNIT IN BIOCHEMISTRY.
DEPARTMENT OF NEUROLOGY AND NEUROPHYSIOLOGY.
FAMILY MEDICINE UNITS NUMBER 20, 41 AND 44, IMSS, CDMX.
SPECIALTY OF HUMAN ACUPUNCTURE OF THE ENMH OF THE IPN

Official Title of the study:

“Evaluation of the effect of electroacupuncture on the sensory symptoms of Symmetrical Distal Polyneuropathy of Diabetic origin and its correlation with changes in Nerve Conduction Velocity.”

MEXICAN SOCIAL SECURITY INSTITUTE AND EDUCATION,
RESEARCH AND HEALTH POLICY UNIT STUDY VERIFICATION ID:
R-2020-785-070.
CONBIOÉTICA-09-CEI-009-20160601.

NCT Number: NOT AVAILABLE.

STATISTICAL ANALYSIS
DATE: August 24th, 2022.

A) CALCULATION OF THE SAMPLE SIZE

The calculation of the sample is based on research questions, this is on the effect of electroacupuncture and expected outcomes in relieving sensory symptoms, on changes in sensory and motor VCN and on the patient's quality of life. Therefore, the development of the sample size calculation will be for each outcome variable and in the end the calculations were concentrated in a summary table. We have suggested taking the highest value to be able to have the certainty of having sufficient statistical power and to be able to find all the differences of the proposed average comparisons.

Sample sizes:

1. For the third outcome, related to "relief". Will electroacupuncture be useful in relieving the sensory symptoms produced by PNDs of diabetic origin?

Table 1 of the review of Thakral G et al. (J Diabetes Sci Technol. 2013, 1;7(5):1202-9) was used as a reference, where different reports of the response and usefulness of electrical stimulation as a complementary treatment of painful and sensory diabetic neuropathy were analyzed and compared, according to this analysis the work of Dinesh Kumar et al. (Diabetes Care 1998, 21 (8): 1322-1325). Where we take into account the reported decrease in neuropathic symptoms with the use of electrical stimulation ($66 \pm 10\%$) when compared to a Sham ($55 \pm 12\%$). For the calculation of the N we use the comparison of means. ^{73,74}

	$n = K [(s_1)^2 + (s_2)^2] / (M_1 - M_2)^2$
K	14.884164 (Za+Zb) ²
s1	10 Standard deviation of group 1
s2	12 Standard deviation of group 2
m1	66 Group 1 Average
m2	55 Group 2 Average
n per group=	30
n total=	60

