The statistical methods to be used will be two-tailed t-tests for comparison of mean value between groups, paired t-tests will be used for comparison of mean values within groups, and repeated two-way analysis of variance for changes in NCV, pain threshold and glucose concentrations.

To evaluate the degree of association between variables and covariates, univariate and bivariate models will be used using the X² test or Fisher's exact test for discrete variables; or the Student's t test, for continuous variables.

The analysis of these tests will be carried out by means of the Mann-Whitney U statistical test, or by means of ANOVA-type statistical measurement. Correlation studies will be performed by Pearson or Spearman Test.

A multivariate analysis will be carried out including the confounding variables (age, time of evolution of DM, anthropometric and biochemical parameters) using a non-conditional logistic regression model, for discrete dependent variables; and a linear regression model for continuous dependent variables.

The analysis of clinical improvement by means of the MDNS scale, the MNSI and the SF-36 will be performed by means of the Mann-Whitney U statistical test. The analysis of nerve conduction velocities shall be carried out by means of ANOVA-type statistical measurement.

It is contemplated to perform an analysis of multiple results and by subgroups, that is, by stratification according to age, time of diagnosis of DM, degree of affection, scale of pain and type of conventional pharmacological treatment, evaluating sensation and perception of the stimulus of pain, vibration, reflexes, VCN by electrophysiological techniques.

Although both groups may have improvement due to conventional treatment, significant differences or trends in the electroacupuncture group are expected, the analysis will include logistic regression analyzing the confounding variables.

For all tests a value of $p < 0.05$ shall be considered statistically significant.

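### The correlation named in the title has only a bivariate Pearson or Spearman test, with arm handling not fixed; if the arms are pooled, treatment effects on both measures can make it significant with no within-arm link

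*SAP*

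**What the plan says.** The official title gives the aim as the effect of electroacupuncture on sensory symptoms "and its correlation with changes in Nerve Conduction Velocity". Under the heading Statistical Analysis, one sentence covers the method: "Correlation studies will be performed by Pearson or Spearman Test". It does not state which symptom score and which NCV measure are correlated, whether these are levels or changes, over which period, or in which patients.

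Nothing else in that section brings randomised arm into the correlation:

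- **Adjusted models.** "A multivariate analysis will be carried out including the confounding variables (age, time of evolution of DM, anthropometric and biochemical parameters"; arm is not among the listed terms, and the models are not linked to the correlation.
- **Subgroups.** These are formed "by stratification according to age, time of diagnosis of DM, degree of affection, scale of pain and type of conventional pharmacological treatment"; arm is not a factor.
- **Expectation.** "significant differences or trends in the electroacupuncture group are expected".
- **Significance.** "For all tests a value of $p < 0.05$ shall be considered statistically significant".

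The sample size section plans for an effect of electroacupuncture against sham on both sensory symptoms and NCV.

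**The concern.** A Pearson or Spearman coefficient has no place for a grouping variable. In a two-arm trial in which treatment moves both measures, treated patients tend to sit high on both and sham patients low on both. That alone produces a correlation across the combined sample, even if, among patients given the same treatment, those with more symptom relief show no more NCV change than the others.

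What is at stake is interpretation. A significant pooled coefficient would invite the conclusion that symptom relief tracks nerve recovery in individual patients. It may add nothing to the two between-arm comparisons already planned. The problem grows with the success of the treatment, so it is most likely to arise in the situation the SAP expects. Leaving arm handling open also allows the choice between pooled, by-arm and adjusted coefficients to be made after the data are seen.

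**Working it through.** The SAP gives no coefficient, sample size or power for the correlation, so there is no figure of its own to reproduce on this point. As a check on the planning inputs, its relief calculation does reproduce: 14.884164 × (10² + 12²) / (66 − 55)² = 30.01, stated as 30 per group.

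**Inputs**

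- Symptom effect, from item 1 of the sample size section (66 ± 10 against 55 ± 12): d1 = 11 / √((100 + 144)/2) = 11 / 11.05 = 0.996 SD.
- NCV effect. The SAP gives no usable between-arm figure, so three values are taken as assumptions:
  - 0.283 SD, back-solved from the 196 per group at 95% confidence and 80% power in item 2: √(2 × 7.849/196), with 7.849 = (1.960 + 0.842)².
  - 0.523 SD, back-solved from the 109 per group in the summary table: √(2 × 14.884/109).
  - 3.07 SD, from 48.2 ± 0.6 and 46.2 ± 0.7 in item 2: 2 / √((0.36 + 0.49)/2) = 2/0.652. Item 2 describes these as values at the start and end of the intervention, so using them as an arm difference is an assumption.
- The two back-solved values are only as good as their sources. The NCV inputs put into the SAP's formula give 14.884 × 0.85/4 = 3.2 per group (1.7 at 95%/80%), so neither 196 nor 109 follows from them.
- 109 per arm (218 in total), test at 0.05. Two-sided testing is assumed for the correlation; the SAP states it only for the "two-tailed t-tests for comparison of mean value between groups".

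**Formula.** With equal arms, zero within-arm correlation and standardised arm effects d1 and d2, the expected pooled coefficient is

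r = (d1·d2/4) / √((1 + d1²/4)(1 + d2²/4)).

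For d1 = 0.996 and d2 = 0.283: (0.0705) / √(1.248 × 1.020) = 0.062. The rejection rate follows approximately from Fisher's transformation: 0.0626 × √215 = 0.92, so P(Z > 1.04) + P(Z < −2.88) ≈ 0.15. For d2 = 0.523: r = 0.113, 0.1132 × √215 = 1.66, P(Z > 0.30) ≈ 0.38.

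**Results at 109 per arm, no within-arm association** (rates from simulation, 4,000 runs per scenario, except the 0.283 row, where the pooled rate is the approximation above, confirmed by simulation)

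| Symptom d | NCV d | Expected pooled r | Pooled Pearson rejects | Adjusted for arm |
|---|---|---|---|---|
| 0.996 | 0 | 0 | 5% | 5% |
| 0.3 | 0.3 | 0.02 | 6% | 5% |
| 0.5 | 0.5 | 0.06 | 13% | 5% |
| 0.996 | 0.283 | 0.06 | 15% | about 5% |
| 0.996 | 0.523 | 0.11 | 38–40% | 5% |
| 0.8 | 0.8 | 0.14 | 54% | 5% |
| 0.996 | 3.07 | 0.37 | 100% | 5% |

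The 38–40% is the spread between separate simulation runs. Spearman behaves almost identically (39% and 100% for the 0.523 and 3.07 rows), so choosing ranks does not help. With 131 per arm the pooled rates are somewhat higher, for example 44% for the 0.523 row. The adjusted test stays near 5% in every row because subtracting the arm means removes the treatment effects completely. A coefficient computed within one arm of 109 also rejects in about 5%.

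**The case against.** The strongest reply is that the SAP does not say the arms are pooled. A reader might infer that it does, and so conclude that the stated method cannot answer the title question. The document does not support that. The title concerns the effect of electroacupuncture, and a Pearson or Spearman test within the electroacupuncture arm is a natural reading, uses exactly the stated method, and holds its 5% level. This stands: the defect is that arm handling is not fixed, not that a wrong handling is prescribed.

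Second, if treatment shifts both measures, the pooled correlation really is non-zero, so the test detects something true. Calling it a false positive presumes that the question is the within-arm link. This also stands as a matter of wording. The error would lie in interpretation, and the SAP does not announce that interpretation.

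Third, a reader might infer from the SAP's figures that a spurious result is close to certain. That rests on the 3.07 SD value, which is a before/after contrast with standard deviations of levels, not of changes. The other two NCV effects are back-solved from sample sizes that disagree with each other. With both effects at 0.3 SD or less there is practically no inflation.

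Fourth, the correlation is not one of the three outcome questions that size the trial, and the between-arm comparisons do not depend on it. That limits the weight of the point. It does not remove it, because the correlation is in the title and one sentence is all that governs it.

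**Conclusion.** The point holds in a conditional form. The plan names a title aim, gives it a bivariate test without an arm term, and leaves open whether the arms are combined. If they are, and if electroacupuncture has moderate or large effects on both measures, a significant coefficient can arise with no link between symptom change and NCV change within either arm.

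With the SAP's symptom effect of 1.00 SD, the chance is about 15% to 38% for the two back-solved NCV effects. It reaches about 100% only if the before/after figures are read as an arm difference. It falls to about 6% when both effects are 0.3 SD and to the nominal 5% when only one measure responds. These figures assume normal data, equal arms of 109, a two-sided 0.05 test and exactly zero within-arm correlation. The sign of the coefficient depends on how improvement is coded.

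The sentence should be corrected before analysis. The main treatment comparisons are not affected.

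**What to change.** Replace the single sentence on correlation with a short specification:

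1. Name the two change scores (one symptom score, one NCV measure), the time points and the direction of coding.
2. Test their association adjusted for arm. Suitable methods are a partial Pearson correlation given arm, its rank-based counterpart if the distribution calls for it, or a linear regression of symptom change on NCV change plus arm.
3. Report the coefficient within each arm.
4. Show any pooled coefficient as descriptive only, without a p-value being read as evidence of a patient-level link.

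Baseline covariates and an arm-by-NCV-change interaction are optional additions. The cost is one degree of freedom for arm, a paragraph of SAP text and a few lines of SPSS syntax. No new data are needed.

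### No between-arm analysis in the SAP adjusts the scales, the NRS or NCV for the outcome's own baseline value, which costs precision but not validity

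*SAP*

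**What the plan says.** All the relevant text is in the SAP's Statistical Analysis section and its Table 1 (categorization of variables).

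- **Scales.** Clinical improvement on the "MDNS scale, the MNSI and the SF-36 will be performed by means of the Mann-Whitney U statistical test". The quantity that enters the test is not defined further.
- **NCV.** One sentence plans "repeated two-way analysis of variance for changes in NCV, pain threshold and glucose concentrations"; a later one says "The analysis of nerve conduction velocities shall be carried out by means of ANOVA-type statistical measurement".
- **General tests.** Two-tailed t-tests compare means between groups, and "paired t-tests will be used for comparison of mean values within groups". No outcome-specific sentence names the NRS.
- **Adjusted models.** A multivariate analysis is planned "including the confounding variables (age, time of evolution of DM, anthropometric and biochemical parameters"), "using a non-conditional logistic regression model, for discrete dependent variables" and linear regression for continuous ones. The section later adds that "the analysis will include logistic regression analyzing the confounding variables".
- **Confounders in Table 1.** Age, fasting glucose, glycosylated haemoglobin, diabetes duration, BMI and pressure.
- **Subgroups.** Degree of affection and the pain scale are named as strata, but only for subgroup analysis.

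**The concern.** In a trial with before and after measurements, the outcome's own baseline value is usually the most prognostic covariate available. The paired within-group tests only make sense if that value is recorded, yet it is absent from every between-arm model of the scales, the NRS and NCV. The models adjust instead for variables that are likely to be less closely related to the outcome.

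Two things follow. Intervals for the electroacupuncture versus sham difference may be wider than they need be, and chance baseline imbalance is not corrected by regression. For the scales, the SAP names a test without fixing whether it is applied to the follow-up score or to the change.

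**Working it through.** **1. Does any planned analysis adjust for the outcome's baseline?**

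| Outcome | Between-arm analysis | Role of its baseline value |
|---|---|---|
| MDNS, MNSI, SF-36 | Mann-Whitney U | None as a covariate; at most inside a change score |
| NRS | Not named; general t-test applies | None stated |
| NCV | Repeated two-way ANOVA | At most one level of the time factor |
| Any of these, regression | Logistic or linear, listed confounders | Not in the list |

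With two time points, the group-by-time test in the ANOVA is the comparison of mean change. That uses baseline but does not adjust for it. Glucose is a possible exception, because biochemical parameters could include its baseline value. There is no such exception for the scales, the NRS or NCV.

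**2. The SAP's own SF-36 figure.** K = (2.576 + 1.282)² = 14.884164. Then n = 14.884164 × (7.37² + 27.7²) / (31.5 − 18.9)² = 14.884164 × 821.61 / 158.76 = 77.03, which reproduces the stated 77 per group. The formula compares two means without baseline information.

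**3. Power at the planned effects.** Inputs: 109 per arm (the size the SAP adopts before losses) and two-sided 0.05 (its analysis threshold).

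- Relief: d = 11 / √((10² + 12²)/2) = 1.0; power about 100%.
- NCV: d = 2 / √((0.6² + 0.7²)/2) = 3.1; power about 100%.
- SF-36: d = 12.6 / √((7.37² + 27.7²)/2) = 0.62; power 0.9955 on follow-up, or on change at r = 0.5, and 0.9995 with adjustment at r = 0.5.

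At these effects, adjustment has almost no power left to add.

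**4. Precision under normal theory.** Let σ² be the outcome variance and r the correlation between baseline and follow-up. The SAP gives no r, so 0.5 to 0.7 is assumed. The variance terms are σ² for follow-up only, 2(1 − r)σ² for change and (1 − r²)σ² with baseline adjustment.

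| | r = 0.5 | r = 0.7 |
|---|---|---|
| Adjusted / change = (1 + r)/2 | 0.75 | 0.85 |
| Interval width against change (square root) | 0.866 | 0.922 |
| 109 per arm acts like | 109/0.75 = 145 | 109/0.85 = 128 |
| Adjusted / follow-up = 1 − r² | 0.75 | 0.51 |

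The variance reduction is 25% to 15% against change (intervals 13% to 8% narrower) and 25% to 49% against follow-up only.

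**5. In SF-36 points.** SD 27.7 is assumed in both arms. With 109 per arm, 80% power needs 0.381 SD.

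- Follow-up only: 0.381 × 27.7 = 10.56 (0.381 is rounded).
- Change: 10.56 × √(2(1 − r)) = 10.56 (r = 0.5) or 8.18 (r = 0.7).
- Adjusted: 10.56 × √(1 − r²) = 9.14 or 7.54.

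**6. Does this carry over to skewed, bounded scores?** Only partly. Power was simulated for a 0 to 100 score (mean 31.5, SD 27.7) with an assumed difference of 9 points.

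| Simulation | r | Mann-Whitney, follow-up | Linear, arm + baseline | Rank-based, baseline-adjusted |
|---|---|---|---|---|
| A | 0.5 | 0.74 | 0.77 | not run |
| A | 0.7 | 0.74 | 0.89 | not run |
| B | 0.3 | 0.81 | 0.69 | 0.84 |
| B | 0.5 | 0.79 | 0.74 | 0.89 |

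In simulation A, Mann-Whitney on change had power 0.66 (r = 0.5) and 0.86 (r = 0.7). At r = 0.5 the order of the first two methods reverses between the simulations; it depends on how the treatment effect is imposed on the bounded score. A linear model therefore cannot be relied on to beat Mann-Whitney on follow-up for such scores. The rank-based adjusted model beat it wherever both were run.

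**The case against.** The strongest reply is that nothing here is an error. Randomisation makes Mann-Whitney, the t-test and the repeated ANOVA valid without a baseline covariate, and power at the planned effects is above 99%. The gain rests on an assumed correlation and on a 9-point effect that the SAP does not plan for. All of that stands, and it limits the point to efficiency and pre-specification. It also stands that normal-theory gains must not be promised for the skewed scales.

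Four stronger readings are tempting, and the SAP supports none of them.

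- **That the comparison is biased, or ignores baseline altogether.** Omitting a baseline covariate does not bias a randomised comparison. The repeated ANOVA uses baseline through time if baseline is one of its time points, and severity appears among the subgroup strata.
- **That the NRS or the MNSI symptom score will be split into yes/no.** Table 1 types both as discrete quantitative, and discrete outcomes go to logistic regression. But Table 1 also types age and BMI as discrete, so its labels are no safe guide to the model, and no cut-point is stated anywhere.
- **That the scale endpoint is wholly open.** The word improvement leans towards change, and the exact definition may stand in the protocol, which is not at hand. Choosing the better of follow-up and change after seeing the data would raise a 5% error to about 9%. That is a worst case, and nothing in the SAP says it would be done.
- **That the NCV sample-size section shows when this trial measures NCV.** Its start and end values come from a cited study. The evidence that baseline is collected here is the planned paired tests.

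**Conclusion.** The point holds as a recommended improvement. For MDNS, MNSI, SF-36, the NRS and NCV, the SAP plans no between-arm analysis adjusted for the outcome's own baseline value, and it leaves improvement on the scales undefined.

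The cost is wider intervals and less power for effects smaller than those planned. Against change, or a two-time-point group-by-time ANOVA, it is a variance 25% to 15% larger than need be when expressed as the reduction available; against follow-up only, that reduction is 25% to 49%. These figures assume normal theory, equal variances and r of 0.5 to 0.7. The percentages do not depend on the 109 per arm. On skewed, bounded scores the benefit depends on the model, and a linear one may bring none over Mann-Whitney on follow-up.

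**What to change.** Add to the Statistical Analysis section:

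- **NCV and NRS.** The main between-arm analysis is a linear model of the end-of-intervention value on randomised arm and that outcome's baseline value, reported as an adjusted mean difference with 95% CI.
- **MDNS, MNSI and SF-36.** The main analysis is a baseline-adjusted rank-based or proportional-odds model of the end-of-intervention value on arm and baseline. Name one of the two for each scale before the data are seen. This respects the ordinal typing in Table 1 and settles the follow-up or change question.
- **Sensitivity analyses.** Keep Mann-Whitney, stated to be on change, for the scales and the repeated two-way ANOVA for NCV.
- **Within-arm paired tests.** Label them descriptive. The SAP itself expects as much: "Although both groups may have improvement due to conventional treatment", so improvement within an arm does not show an effect of electroacupuncture.

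The cost is SAP wording and standard models on data already collected. No patients, visits or procedures are added.

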Za	2.576
Zb	1.282

For this research question a total of 60 subjects will be required, 30 for each group under study.

2. For the second outcome, will the use of electroacupuncture generate changes in the study of sensory and motor NCV by electrophysiological techniques?

For the question, it is calculated considering the mean and SD resulting at the beginning and end of the intervention of the changes of the NCV of Yanqing Tong et al. of 48.2 ± 0.6 vs 46.2 ± 0.7 (m / s).⁶¹ A comparison of means was made, with the test assumption of a bilateral hypothesis, with a Confidence or Security Level (1- α): 95%, Statistical Power of 80%, Accuracy (d) of 20%, the resulting sample size was:

196 subjects per group

3. For the third outcome, will the use of electroacupuncture generate improvement in the evaluation of the patient's quality of life as measured by the SF36?

So far there is no publication that analyzes the perception of an improvement in quality of life in subjects with diabetic neuropathy with the use of electroacupuncture. Therefore, we have raised the size according to those described in the article by *Kongkiat Kulkantrakorn et al.*⁷⁵ where the aforementioned authors made a "baseline" estimate of the perception of the quality of life of the patient with diabetic foot in 8 domains of the SF-36. Our proposal is that there will be an improvement in the quality of life, in all the domains described, that is, it will be at least equal or better, we have taken into account the average of the physical function which is the deteriorated of 18.9.

Table 4: Comparison of SF-36 mean score in relevant studies

Domains	Multiple sclerosis* (N=85)	Epilepsy* (N=271)	Diabetes* (N=555)	Diabetic foot ulcer [†] (Thailand) (N=40)	Healthy Thai adults [‡] (N=1,345)	PDN current study (N=33) [§]	Current study [§] VS Healthy Thai adults [‡] (P value)
Physical function	33.5	78.9	74.2	18.9	77.3±17.4	31.5±27.7	<0.001 [†]
Role limitation due to physical problem	32.7	60.0	55.1	27.5	82.2±28.6	40.2±39.0	<0.001 [†]
Bodily pain	72.2	72.8	71.7	32.5	75.6±18.4	47.3±30.6	<0.001 [†]
General health	53.7	68.7	52.6	79.5	65.1±18.1	50.8±28.5	0.007 [†]
Vitality	41.9	55.4	54.3	70.9	62.2±13.3	60.9±35.9	0.63
Social functioning	60.2	77.3	81.2	50.9	78.2±18.2	63.6±29.7	0.008 [†]
Role limitation due to emotional problem	59.6	66.3	70.2	51.6	80.4±31.9	42.4±43.5	<0.001 [†]
Emotional well being	67.8	68.4	73.0	36.6	66.1±12.9	39.4±30.7	<0.001 [†]

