*Reference 22; [†]Reference 20; [‡]Reference 8; [§]Current study; [†]Statistically significant; PDN: Painful diabetic neuropathy; SF-36: Short form 36 quality of life questionnaires

Table taken from J Neurosci Rural Pract. 2013 Jul-Sep; 4(3): 267–270.⁷⁵

Making a comparison of averages:

$$n = K [(s1)^2 + (s2)^2] / (M1 - M2)^2$$

K	14.884164	(Za+Zb) ²
s1	7.37	Standard deviation of group 1
s2	27.7	Standard deviation of group 2
m1	31.5	Group 1 Average
m2	18.9	Group 2 Average
n per group=	77	
n total=	154	
Za	2.576	
Zb	1.282	

NOTE: As we discussed previously, we have suggested taking the highest value in order to be sure of having sufficient statistical power and to find all the differences in the proposed mean comparisons of each outcome (that is, the effect of Electroacupuncture compared to sham on the following outcome variables).

Each group was added 20% of the N for possible losses.

OUTCOME VARIABLE	N PER GROUP	ALPHA Z	Z DE BETA	PLUS 20% OF POSSIBLE LOSSES PER GROUP	STUDY TOTAL
Relief of sensory symptoms	30	2.576	1.282	36 Total :36	72
Changes in the study of sensory and motor VCN	109	2.576	1.282	130.8 Total: 131	262
Improvement in quality of life assessment	77	2.576	1.282	92.4 Total: 93	186

The sample of the present study was estimated at 109 for each group, however, 20% was added considering possible losses (each group will be 131), therefore, the total N of the study is 262.

It is important to mention that the way to obtain the sample will be by number of consecutive cases of candidate patients who go to the outpatient consultation of the UMF 20, 41 and 44 of the IMSS of the CDMX, for their subsequent evaluation in the screening and respective randomization in case of being included in the study.

VARIABLES

TABLE 1. CATEGORIZATION OF VARIABLES

	VARIABLE	MEASURING INSTRUMENT	TYPE AND SCALE OF MEASUREMENT	UNITS
DEPENDENT	Sensitive commitment	MDNS	Ordinal qualitative	Normal, diminished and absent
	Brawn	MDNS	Ordinal qualitative	Normal, moderate, severe and absent
	Reflexes	MDNS	Ordinal qualitative	Present, present with effort and absent.
	Sensory symptoms	MNSI	Discrete Quantitative	Dichotomous Response (Yes, No) Evaluation score 13 out of 15
	Aquilian reflex	MNSI	Ordinal qualitative	Present, present with effort and absent.
	Vibration perception	MNSI	Ordinal qualitative	Present, present with effort and absent.
	Pain scale	NRS	Discrete Quantitative	Evaluation score 0-10

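### The NCV sizing, which sets total N, is stated in two conflicting ways (196 per group at 5%/80%; 109 at 1%/90%), and neither follows from the quoted inputs; the blanket p<0.05 rule also needs a stated success criterion

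*SAP*

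**What the plan says.** **Sizing.** Section A of the SAP, Calculation of the sample size, sizes three outcomes: relief of sensory symptoms, NCV and SF-36 quality of life. Its introduction gives the rule for combining them: "We have suggested taking the highest value to be able to have the certainty of having sufficient statistical power". The NOTE before the summary table repeats the rule and adds the aim "to find all the differences in the proposed mean comparisons of each outcome".

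For NCV, item 2 quotes 48.2 ± 0.6 against 46.2 ± 0.7 m/s, described as values at the start and end of an intervention. It sets a two-sided test with "95%, Statistical Power of 80%, Accuracy (d) of 20%, the resulting sample size was" followed by "196 subjects per group". The NCV row of the summary table reads "Changes in the study of sensory and motor VCN 109 2.576 1.282". The closing text follows the table: "The sample of the present study was estimated at 109 for each group", raised by 20% to 131 per group and 262 in total.

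**Testing.** The Statistical Analysis section ends with "For all tests a value of $p < 0.05$ shall be considered statistically significant". The same section says "It is contemplated to perform an analysis of multiple results and by subgroups", and names five stratifying factors: age, time since diagnosis, degree of affection, pain scale and type of drug treatment. The SAP gives no testing order and no adjustment.

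**The concern.** NCV has the largest n in the summary table, so it alone determines the size of the trial. Its alpha, its power and its n all differ between the text and the table. A reader cannot tell what effect the trial is designed to detect on NCV, or with what power.

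A separate and weaker question is what the blanket 0.05 threshold means. Three outcomes are sized separately, and further variables and subgroups are tested at the same level. Whether this inflates the false-positive risk depends on how many of the three must succeed before an effect is claimed, and the SAP does not say.

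**Working it through.** **1. Reproduce what can be reproduced.** The SAP's formula is n per group = K(s1² + s2²)/(M1 − M2)², with K = (2.576 + 1.282)² = 14.884. A Z of 2.576 is two-sided alpha 0.010, and a Z of 1.282 is power 0.900.

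- Relief (66 ± 10 against 55 ± 12): 14.884 × (100 + 144)/11² = 30.01. Stated: 30.
- SF-36 (31.5 against 18.9; SDs 7.37 and 27.7): 14.884 × (54.32 + 767.29)/12.6² = 77.03. Stated: 77.
- Losses: 109 × 1.2 = 130.8, so 131 per group and 262 in total, as stated.

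**2. Apply the same formula to NCV.** The inputs are SDs 0.6 and 0.7 and a difference of 2.0, so (0.36 + 0.49)/4 = 0.2125.

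- At 5%/80%, K = (1.96 + 0.8416)² = 7.849, and n = 1.67, rounded up to 2. Stated in item 2: 196.
- At 1%/90%, K = 14.884, and n = 3.16, rounded up to 4. Stated in the table: 109.

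**3. Direction of the change.** From 5%/80% to 1%/90%, n should rise by 14.884/7.849 = 1.90. On that basis 196 would become about 372. The table instead shows a fall to 109.

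**4. Where 196 may come from (inference).** Reading the stated accuracy d of 20% as 0.2 SD, (1.96 + 0.84)²/0.2² = 7.84/0.04 = 196.0. This is a one-sample or paired form, which would fit the before-after source of the means. A two-arm comparison with an effect of 0.2 SD at 5%/80% needs 2 × 7.849/0.04 = 392.4, so 393 per group before losses. No calculation tried on the stated NCV inputs gave 109.

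**5. NCV power at 109 per group.** For a simple two-arm comparison of means, two-sided 0.05, normal approximation: power = Φ(effect × √(109/2) − 1.96), with √54.5 = 7.382.

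| Assumed between-arm effect | Basis | Power |
|---|---|---|
| 0.2 SD | d of 20% read as SD units | Φ(1.476 − 1.96) = 31% |
| 0.283 SD | 196 read as a two-arm 5%/80% size: 2.8016 × √(2/196) | Φ(2.089 − 1.96) = 55% |
| 0.523 SD | 109 read as a two-arm 1%/90% size: 3.858 × √(2/109) | Φ(3.858 − 1.96) = 97% |

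On the quoted 2.0 m/s and SDs of 0.6 and 0.7, power would be practically 100%. That is why those inputs cannot have produced either n.

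**6. Testing rule, if any one of three suffices.** With no effect on any outcome and each tested at 0.05, the chance of at least one false positive is 1 − 0.95³ = 14.3% under independence. With equicorrelated normal test statistics it is 12.5% at a correlation of 0.5 and 10.9% at 0.7; both correlations are assumptions.

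**7. Price of the strictest Holm step.** 0.05/3 = 0.0167, z = 2.394, with 109 per group.

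- Relief: 11/√(244/109) = 7.35; power over 99.9%.
- SF-36: 12.6/√(821.6/109) = 4.59; Φ(4.59 − 2.394) = 98.6%.
- SF-36 with both SDs at 27.7 (an assumption, since 7.37 is not explained): 12.6/√(1534.6/109) = 3.36; Φ(3.36 − 2.394) = 83%.

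**The case against.** **On NCV**, one could blame a slip in copying or in PDF conversion. That does not stand: 109, 130.8, 131 and 262 agree with one another, the prose repeats 109, and alpha and power differ along with n. A reader might go further and infer that the trial is underpowered, or that the right total is 472 (196 × 1.2 = 235.2, so 236 per group). The SAP supports neither. 472 presumes that 196 is a valid two-arm size, and step 4 suggests that it may not be. Nor are 55% and 97% bounds, since 0.2 SD gives 31%. The true design effect is simply not on the page.

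**On testing**, the opposing case is stronger. The SAP poses three separate research questions, each with its own sizing. Testing each at 5% is defensible when no joint claim is made. A primary outcome and success rule are commonly set in the protocol, which is not at hand. A reader might infer that the trial's false-positive risk is 14.3%, but the SAP nowhere says that one significant outcome is enough. An aim of finding every difference does not say so either. What remains is that the SAP itself fixes one unadjusted threshold for every test, so its scope should be clarified.

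The 1% level used to size relief and SF-36, against 5% in the analysis, might also look like an error. It is conservative for power and is not part of this point.

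The low price of Holm should not be oversold. The SF-36 difference of 12.6 is a gap between two patient populations in a published table (painful neuropathy and foot ulcer), not a treatment effect. The powers above are also for simple comparisons of means, whereas the SAP plans Mann-Whitney tests for SF-36 and ANOVA for NCV.

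**Conclusion.** The NCV sizing is wrong as written. The SAP gives two incompatible sets of alpha, power and n for the outcome that sets N. Neither n follows from the quoted data, and the lower one is used despite the rule to take the highest. This rests only on the SAP's text and arithmetic. The one-sample origin of 196 is an inference, and the power range of 31% to 97% depends on assumed effects.

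The testing point is secondary and conditional. The risk of 10.9% to 14.3% applies only if any one of the three sized outcomes can support a claim and none has a true effect. If all three must succeed, there is no inflation. The sponsor should act on both points; the NCV contradiction carries the weight.

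**What to change.** **NCV.** State one alpha, one power, and one between-arm difference with its SD. Show the calculation, and make item 2, the summary table and the final N agree. If N stays at 262, restate the effect and power that 109 per group delivers. This costs only wording if 109 can be justified. Otherwise N may change, by an amount that cannot be given until the effect is fixed.

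**Testing.** State whether one, or all, of the three sized outcomes must be significant for a claim of effect. If all, say so and leave 0.05 as it is. If any one suffices, name one between-arm variable per sized outcome before the data are analysed, and apply Holm at overall two-sided 0.05: smallest p against 0.0167, next against 0.025, last against 0.05, stopping at the first failure. If the protocol names a primary outcome, test it first at 0.05 and apply Holm to the other two only if it succeeds. Other multiplicity procedures would also serve. Report remaining variables and subgroups as exploratory.

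This part needs SAP wording only. Its downside is the stricter first threshold. On the SAP's inputs the loss is small for relief and SF-36, with the reservations above; for NCV it cannot be stated until the sizing is reconciled.
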